5.5 Definition of Dose-Limiting Toxicity

Dose-limiting toxicity (DLT) will be defined as any of the following events, detailed in Sections 5.5.2 and 5.5.3 that are possibly, probably or definitely attributable to protocol therapy. Decisions regarding the estimation of the recommended phase II dose and assigning treatment dosages to subsequent patients will be made on observations occurring in the first cycle of therapy.

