5.5.1 Grading of Adverse Events

Adverse events (toxicities) will be graded according to the NCI Common Terminology Criteria for Adverse Events v4.02 (CTCAE) http://ctep.cancer.gov/reporting/ctc.html.

Any suspected or confirmed dose-limiting toxicity should be reported within 24 hours to the coordinating center and Principal Investigators at both centers.

5.5.2 Non-Hematological Dose-Limiting Toxicity

Non-hematological dose-limiting toxicity is defined as any Grade 3 or Grade 4 nonhematological toxicity that is possibly, probably or definitely attributable to the investigational drugs with the specific exclusion of:

- Grade 3 nausea, vomiting or dehydration
- Grade 3 diarrhea \leq 3 days
- Grade 3 diarrhea regardless of duration if patient did not receive appropriate supportive care (cefixime, loperamide, or atropine as outlined in Section 5.3)
- Grade 3 transaminase (AST/ALT) elevation that returns to grade ≤ 1 or baseline prior to the time for the next treatment cycle
- Grade 3 GGT
- Grade 3 fatigue \leq 3 days
- Grade 3 fever, febrile neutropenia, or infection
- Grade 3 electrolyte abnormalities (Na, K, Cl, CO2, Ca, Mg, Phosphate) that improve to \leq grade 2 within 7 days, with or without supplements

Allergic reactions that necessitate discontinuation of the study drugs will not be considered a dose-limiting toxicity.

Patients who develop \geq Grade 3 QTc prolongation (\geq 501 msec) at any time must be removed from protocol therapy.

5.5.3 Hematological Dose-Limiting Toxicity

Hematologic DLT will be defined as any of the following:

- Greater than 7 days duration of either grade 4 neutropenia or grade 4 thrombocytopenia of > 7 days duration
- Grade 3 or 4 thrombocytopenia that requires platelet transfusions on greater than 2 occasions during a cycle.
- Failure to recover blood counts to eligibility criteria that cause a delay of \geq 14 days between treatment cycles.

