5.6 Dose Escalating Criteria

A 3 + 3 design will be used to determine dose assignment for patients, as described in Section 13.2. Specifically, the following rules will apply for dose escalation:

- A. Evaluate 3 patients at $dose_k$:
 - 1. If 0 of 3 patients have DLT, then
 - i. If first cohort, increase dose to $dose_{k+1}$ and go to A.
 - ii. Otherwise, go to B.
 - 2. If 1 of 3 patients has DLT, then go to B.
 - 3. If more than 1 patient has DLT
 - i. If lowest dose, then go to C.
 - ii. Otherwise, decrease dose to $dose_{k-1}$ and go to A.
- B. Evaluate 3 additional patients at dose_k :
 - 1. If 0 or 1 of 6 patients has DLT, then increase dose to $dose_{k+1}$ and go to A.
 - 2. If 2 or more patients have DLT, then
 - i. If lowest dose, then go to C.
 - ii. Otherwise, decrease dose to $dose_{k-1}$ and go to A.
- C. Discontinue dose escalation/de-escalation.

Accrual will continue until the recommended phase II dose for a Phase II study (RP2D) is established and at least 6 patients have been treated at this dose. The RP2D is the highest dose level at which no more than 1 of 6 patients experiences first-cycle DLT. Doses higher than dose level 2 will not be studied in this trial. Once the RP2D is identified, an additional 10 patients will be enrolled at this dose level.

5.7 **Duration of Therapy**

In the absence of treatment delays due to adverse event(s), treatment may continue for up to 17 cycles until one of the following criteria applies:

• Disease progression

- Intercurrent illness that prevents further administration of treatment
- Unacceptable adverse event(s)
- Patient decides to withdraw from the study
- General or specific changes in the patient's condition render the patient unacceptable for further treatment in the judgment of the investigator.

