5.9 Criteria for Removal from Protocol Therapy

- a. Clinical or radiographic progressive disease (See Section 11).
- b. Adverse events requiring removal from study (See Sections 6.1 and 6.2).
- c. Refusal of further protocol therapy by patient/parent/guardian.
- d. Non-compliance that in the opinion of the investigator does not allow for ongoing participation.
- e. Completion of 17 cycles of therapy.
- f. Determination that it is not in the patient's best interest by the treating physician.

Patients who are off protocol therapy are to be followed until they meet the criteria for Off Study (see below). Ongoing adverse events, or adverse events that emerge after the patient is removed from protocol therapy, but within 30 days of the last dose of investigational agent, must be followed and reported. Follow-up data will be required unless consent is withdrawn.

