6.1 Dose Modifications for Hematological Toxicity

Patients who experience dose-limiting toxicity at dose levels 1 or 2 but do not have evidence of disease progression may continue to receive therapy modified as described below.

Patients who experience Grade 3 febrile neutropenia may receive additional cycles of therapy at the same eribulin dose with the optional use of filgrastim/pegfilgrastim support.

Patients who experience DLT at dose level 0 will not receive further therapy on study.

- 6.1.1 Patients who have dose-limiting thrombocytopenia should receive subsequent cycles at the same dose of irinotecan with eribulin reduced to the next lowest dose level.
- 6.1.2 Patients who have dose-limiting neutropenia (Grade 4 neutropenia of > 7 days duration or delay in the start of the next cycle for ≥ 14 days due to neutropenia) with no other dose-limiting toxicity should receive the same dose in the next cycle with filgrastim or pegfilgrastim support at standard doses. [Note: Patients MUST NOT receive prophylactic filgrastim or pegfilgrastim in the first cycle of therapy.] If dose-limiting neutropenia recurs after growth factor is added, then the eribulin dose should be decreased to the next lowest dose level and filgrastim/pegfilgrastim support used again.
- 6.1.3 Patients who experience Grade 4 febrile neutropenia may receive additional cycles of therapy at the same eribulin dose with the use of filgrastim/pegfilgrastim support.

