6.2 Dose Modifications for Non-Hematological Toxicity

Patients who experience Grade 3 prolonged QTc (\geq 501 msec) will be removed from protocol therapy.

Patients who experience dose-limiting toxicity at dose levels 1 or 2 but do not have evidence of disease progression may continue to receive therapy modified as described below.

Patients who experience DLT at dose level 0 will not receive further therapy on study

- 6.2.1 Patients who have any dose-limiting non-hematological toxicity (as defined in section 5.5.2) that returns to eligibility criteria within 7 days after the planned start of the next treatment cycle may continue on study but should receive subsequent doses at the next lower dose level of eribulin. If non-hematologic Grade 3 or 4 toxicities other than those listed in Section 5.5.2 recur at a reduced dose, the patient must be removed from protocol therapy.
- 6.2.2 Patients who have any Grade 3 or 4 non-hematological toxicity that does not resolve to eligibility criteria by 7 days after the planned start of the next treatment cycle must be removed from protocol therapy.

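### A patient who stops before about day 36 with unrecovered counts can meet no written DLT criterion, yet stays in the 3+3 denominator

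*Combined protocol and SAP*

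**What the plan says.** Section 5.5 defines DLT as a closed list of attributable events and says that dose decisions "will be made on observations occurring in the first cycle of therapy". Section 5.5.3 gives three hematological items:

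- Prolonged grade 4 cytopenia: "Greater than 7 days duration of either grade 4 neutropenia or grade 4 thrombocytopenia".
- Repeated platelet transfusion, on more than 2 occasions within one cycle, for thrombocytopenia of grade 3 or 4.
- Lack of count recovery: "Failure to recover blood counts to eligibility criteria that cause a delay of" at least 14 days, measured from one treatment cycle to the next.

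The first two can be scored on cycle 1 data alone. The third needs a next cycle to be delayed. Section 6.1.2 restates it for neutropenia in the same terms: "delay in the start of the next cycle for" at least 14 days.

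Section 5.4 bars a further cycle after progression. Section 5.9 also ends therapy for refusal, non-compliance and physician judgement. Section 11.1.1 makes every patient evaluable for toxicity from first treatment, and 13.4 puts everyone who received drug in the safety analysis. Section 5.6 then decides: "The RP2D is the highest dose level at which no more than 1 of 6 patients experiences first-cycle DLT". No section defines who is evaluable for DLT, sets a minimum observation period, or provides for replacement.

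**The concern.** The same blood counts give different results depending on why the patient stopped. A patient waiting for cycle 2 whose platelets stay below 100,000/mcL for 14 days past the planned start scores a DLT. A patient with the same platelets who leaves at day 22 for clinical progression does not, because there is no cycle left to delay. Early stopping is plausible here: section 3.1 admits relapsed or progressed disease with no limit on prior therapies.

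The toxicity affected is the one the plan has most reason to watch. Section 2.2 reports neutropenia in 52% of eribulin patients in the cited phase III trial, grade 4 in 24%. An unscored event can turn 2 of 6 (de-escalate) into 1 of 6 (acceptable), and ten more patients are then treated at the selected dose.

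**Working it through.** The plan states no target DLT rate, early-stopping rate or operating characteristics, so there is no figure of its own to reproduce.

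**Timing.** A 21-day cycle puts planned Day 1 of cycle 2 at day 22. A 14-day delay is complete at 22 + 14 = day 36. This is approximate, since section 5.2 lets the start vary by 3 days. Off-study status under 5.10 comes 30 days after the last dose: 8 + 30 = day 38 if day 8 is given, but 5 + 30 = day 35 if the last dose was on day 5.

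**Who falls through.** All of the following must hold:

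1. The patient stops before about day 36 for a reason that is not itself a DLT.
2. ANC is below 1,000/mcL or platelets are below 100,000/mcL (3.1.6), attributably, and would have stayed there to day 36.
3. There is no grade 4 neutropenia or thrombocytopenia beyond 7 days.
4. There are no more than 2 platelet transfusion occasions.
5. There is no non-hematological DLT.

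This patient meets no item on the list, and nothing removes the patient from the 3 or 6. No sentence says to score zero; that follows from the closed list, 11.1.1 and the absence of an evaluability rule.

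**Effect on the decision.** The chance that a dose passes at most 1 of 6 at DLT rate p is

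P(p) = (1 − p)^6 + 6p(1 − p)^5.

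Stopping early at 2 or more DLTs in the first 3 does not change it. Let f be the share who stop early and r the share whose only DLT is count failure, taken as independent. The scored rate is then p − f·r. Assumed ranges: f = 0.10-0.30, r = 0.10-0.20.

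| True p | All events scored | Low end (f·r = 0.01) | Ceiling (f·r = 0.06) |
|---|---|---|---|
| 0.30 | P(0.30) = 0.1176 + 0.3025 = 42.0% | P(0.29) = 44.2% | P(0.24) = 55.8% |
| 0.33 | P(0.33) = 35.8% | P(0.32) = 37.8% | P(0.27) = 48.7% |

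**Why the upper end is a ceiling.** At p = 0.30 it makes count failure the only DLT in 0.20/0.30 = two thirds of DLT patients. Suppose instead that 20% have count failure, overlapping independently with other DLTs. The other-DLT rate is then 1 − 0.70/0.80 = 0.125, count-only DLTs are 0.20 × 0.875 = 0.175, and the loss is 0.30 × 0.175 = 0.0525. P(0.2475) = 54.0%.

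**A second parameterization.** Let s be the share of DLTs that are count-recovery only (0.25-0.75) and d the share of those patients who stop early (0.1-0.3). The scored rate is p(1 − s·d). At p = 0.33 the pass chance goes from 35.8% to 37.4-52.0%, a similar range.

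**How often one patient decides.** The chance of exactly 2 DLTs in 6 at p = 0.30 is 15 × 0.30² × 0.70⁴ = 32.4%, so the rule often sits one event from reversal.

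**The case against.** The strongest case is that this subgroup is narrow and that several broader readings fail.

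- A reader might infer that such a patient can never score. The 6.1.2 wording allows a patient held 14 days for low counts, who then stops, to be read as having the event. The gap is clear only for stops before about day 36.
- A reader might add QTc removals. Attributable Grade 3 QTc prolongation is not among the 5.5.2 exclusions, so it is already a DLT.
- A reader might treat 6.2.2 as a general route, since its rule ("does not resolve to eligibility criteria by 7 days after the planned start of the next treatment cycle must be removed from protocol therapy") ends treatment before 14 days have passed. That rule concerns Grade 3-4 non-hematological toxicity, most of which already scores under 5.5.2 if attributable. Only a residue remains, such as excluded Grade 3 infection.
- A reader might say recovery is not followed. Section 5.8 follows those removed for adverse events to resolution or stabilization, and 5.9 requires ongoing events to be followed and reported. What lapses is the fixed CBC schedule: after stopping, the calendar has only the off-treatment and off-study counts, and 5.10 ends the study at a new regimen.
- The percentages rest on assumptions. The first scheduled disease evaluation is in cycle 2, so earlier progression must be found clinically, and nothing in the documents supports 30% stopping early.

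All of this limits the scope and size. None of it supplies a rule for the patient described: unrecovered counts seen at follow-up would still not meet the criterion as written.

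It is also fair that the missing evaluability and replacement rule is the broader fault. Rewording 5.5.3 alone would leave the cohort count undefined for a patient lost before the assessment date.

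**Conclusion.** The point stands in limited form. The count-recovery criterion has no stated scoring for a patient who stops before about day 36 with unrecovered counts and no other DLT, and that patient remains in the denominator.

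The direction is certain: omission can only lower the DLT count, which favors the higher eribulin dose. The size is not known. The low end of the assumed range is about 2 percentage points in the chance of passing (42.0% to 44.2% at a 30% rate). The 55.8% figure is a ceiling and should not be read as an estimate. The documents do not support saying that the selected dose will be wrong, or that early stoppers in general escape DLT scoring. Because the primary objective rests on six patients and the correction is small, the plan should be amended.

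**What to change.** Keep the plan's own thresholds and change how the event is anchored.

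- **5.5.3:** define the criterion as attributable ANC or platelets still below the 3.1.6 levels 14 days or more after the planned Day 1 of cycle 2 (about day 36), whether or not another cycle is given. State that it counts as a first-cycle DLT although it is complete after day 21. Align 6.1.2.
- **Section 10, calendar footnote:** patients who stop with unrecovered counts have CBCs until recovery or that date. Existing follow-up reaches day 38 after a day 8 dose. The footnote should name the date itself, because a last dose on day 5 gives only day 35 under 5.10.
- **5.6 and 13.1:** a patient who starts other therapy or is lost before that date, with unrecovered counts and no other DLT, is not counted as DLT-free in the 3 or 6 and is replaced for the dose decision. Such patients stay in the 13.4 safety analysis.

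The cost is a few sentences, a few extra blood counts and an occasional replacement patient. The upper limit of 22 in 13.2 equals 6 + 6 + 10 and leaves no room for replacements on a path that fills two dose levels, so the section should allow for them.

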5.6 Dose Escalating Criteria

A 3 + 3 design will be used to determine dose assignment for patients, as described in Section 13.2. Specifically, the following rules will apply for dose escalation:

- A. Evaluate 3 patients at $dose_k$:
 - 1. If 0 of 3 patients have DLT, then
 - i. If first cohort, increase dose to $dose_{k+1}$ and go to A.
 - ii. Otherwise, go to B.
 - 2. If 1 of 3 patients has DLT, then go to B.
 - 3. If more than 1 patient has DLT
 - i. If lowest dose, then go to C.
 - ii. Otherwise, decrease dose to $dose_{k-1}$ and go to A.
- B. Evaluate 3 additional patients at dose_k :
 - 1. If 0 or 1 of 6 patients has DLT, then increase dose to $dose_{k+1}$ and go to A.
 - 2. If 2 or more patients have DLT, then
 - i. If lowest dose, then go to C.
 - ii. Otherwise, decrease dose to $dose_{k-1}$ and go to A.
- C. Discontinue dose escalation/de-escalation.

Accrual will continue until the recommended phase II dose for a Phase II study (RP2D) is established and at least 6 patients have been treated at this dose. The RP2D is the highest dose level at which no more than 1 of 6 patients experiences first-cycle DLT. Doses higher than dose level 2 will not be studied in this trial. Once the RP2D is identified, an additional 10 patients will be enrolled at this dose level.

5.7 **Duration of Therapy**

In the absence of treatment delays due to adverse event(s), treatment may continue for up to 17 cycles until one of the following criteria applies:

• Disease progression

- Intercurrent illness that prevents further administration of treatment
- Unacceptable adverse event(s)
- Patient decides to withdraw from the study
- General or specific changes in the patient's condition render the patient unacceptable for further treatment in the judgment of the investigator.

5.8 Duration of Follow-Up

Patients removed from study for unacceptable adverse event(s) will be followed until resolution or stabilization of the adverse event. All patients will be followed for at least 30 days after removal from study or until death, whichever occurs first.

5.9 Criteria for Removal from Protocol Therapy

- a. Clinical or radiographic progressive disease (See Section 11).
- b. Adverse events requiring removal from study (See Sections 6.1 and 6.2).
- c. Refusal of further protocol therapy by patient/parent/guardian.
- d. Non-compliance that in the opinion of the investigator does not allow for ongoing participation.
- e. Completion of 17 cycles of therapy.
- f. Determination that it is not in the patient's best interest by the treating physician.

Patients who are off protocol therapy are to be followed until they meet the criteria for Off Study (see below). Ongoing adverse events, or adverse events that emerge after the patient is removed from protocol therapy, but within 30 days of the last dose of investigational agent, must be followed and reported. Follow-up data will be required unless consent is withdrawn.

5.10 Off-Study Criteria

Patients will be considered off-study if any of the following events occur:

- a. Thirty days has expired after the last dose of protocol therapy.
- b. Death
- c. Lost to follow-up
- d. Withdrawal of consent for any further data submission.
- e. Entry onto another antineoplastic therapeutic study.
- f. Onset of new treatment regimen

6. DOSING DELAYS/DOSE MODIFICATIONS

Dose modifications will involve eribulin but not irinotecan, given that the study question is to identify the recommended phase II dose of eribulin that can be safely administered with fixed-dose irinotecan.

Doses which have been reduced for toxicity will not be re-escalated.

6.1 Dose Modifications for Hematological Toxicity

Patients who experience dose-limiting toxicity at dose levels 1 or 2 but do not have evidence of disease progression may continue to receive therapy modified as described below.

Patients who experience Grade 3 febrile neutropenia may receive additional cycles of therapy at the same eribulin dose with the optional use of filgrastim/pegfilgrastim support.

Patients who experience DLT at dose level 0 will not receive further therapy on study.

- 6.1.1 Patients who have dose-limiting thrombocytopenia should receive subsequent cycles at the same dose of irinotecan with eribulin reduced to the next lowest dose level.
- 6.1.2 Patients who have dose-limiting neutropenia (Grade 4 neutropenia of > 7 days duration or delay in the start of the next cycle for ≥ 14 days due to neutropenia) with no other dose-limiting toxicity should receive the same dose in the next cycle with filgrastim or pegfilgrastim support at standard doses. [Note: Patients MUST NOT receive prophylactic filgrastim or pegfilgrastim in the first cycle of therapy.] If dose-limiting neutropenia recurs after growth factor is added, then the eribulin dose should be decreased to the next lowest dose level and filgrastim/pegfilgrastim support used again.
- 6.1.3 Patients who experience Grade 4 febrile neutropenia may receive additional cycles of therapy at the same eribulin dose with the use of filgrastim/pegfilgrastim support.

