13. STATISTICAL CONSIDERATIONS

13.1 Study Design/Endpoints

A phase I, dose-escalation trial is proposed to determine the recommended phase II dose (RP2D) of escalating doses of eribulin in combination with standard-dose oral irinotecan. Cohorts of 3 patients per dose level are proposed using a 3+3 design [70, 71]. The following rules will be incorporated for dose escalation/de-escalation and establishing the recommended Phase II dose using the occurrence of DLT during the first cycle of therapy that is possibly, probably, or definitely attributable to study therapy.

A. Evaluate 3 patients at dose_k:

- 1. If 0 of 3 patients have DLT, then
 - i. If first cohort, increase dose to $dose_{k+1}$ and go to A.
 - ii. Otherwise, go to B.
- 2. If 1 of 3 patients has DLT, then go to B.
- 3. If more than 1 patient has DLT

- i. If lowest dose, then go to C.
- ii. Otherwise, decrease dose to $dose_{k-1}$ and go to A.
- B. Evaluate 3 additional patients at dose_k:
 - 1. If 0 or 1 of 6 patients has DLT, then increase dose to $dose_{k+1}$ and go to A.
 - 2. If 2 or more patients have DLT, then
 - i. If lowest dose, then go to C.
 - ii. Otherwise, decrease dose to $dose_{k-1}$ and go to A.
- C. Discontinue dose escalation/de-escalation.

The RP2D is defined as the highest dose level in which there is no more than 1 DLT in 6 patients. Ten additional patients will be enrolled at the RP2D level. Similar dose modifications as specified in Section 6 would be applied to these patients. Doses higher than dose level 2 will not be studied in this trial.

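### After Grade 4 febrile neutropenia, Section 6.1.3 allows the same eribulin dose while Sections 5.5.2 and 6.2.1 together require the next lower level, and nothing says which governs

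*Combined protocol and SAP*

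**What the plan says.** **DLT definition, Section 5.5.2.** "Non-hematological dose-limiting toxicity is defined as any Grade 3 or Grade 4 nonhematological toxicity" attributable to the study drugs, less a list of exclusions. One exclusion is "Grade 3 fever, febrile neutropenia, or infection". Febrile neutropenia at Grade 4 is not on the list.

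**DLT definition, Section 5.5.3.** The hematological DLTs are prolonged Grade 4 cytopenia ("Greater than 7 days duration of either grade 4 neutropenia or grade 4 thrombocytopenia of > 7 days duration"), thrombocytopenia needing platelet transfusion on more than two occasions in a cycle, and a delay of at least 14 days for count recovery. Febrile neutropenia is not among them.

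**Handling, Section 6.1 (hematological).** An unnumbered sentence lets Grade 3 febrile neutropenia continue at the same eribulin dose with optional growth factor. Item 6.1.3 covers Grade 4: "Patients who experience Grade 4 febrile neutropenia may receive additional cycles of therapy at the same eribulin dose", with growth factor. The opening text of 6.1 also says: "Patients who experience DLT at dose level 0 will not receive further therapy on study". Section 6.2 repeats that sentence.

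**Handling, Section 6.2.1 (non-hematological).** Its scope is every DLT that meets 5.5.2, provided the toxicity recovers within 7 days after the planned start of the next cycle. Such patients "may continue on study but should receive subsequent doses at the next lower dose level of eribulin".

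**Use of the DLT count, Section 13.1.** "The RP2D is defined as the highest dose level in which there is no more than 1 DLT in 6 patients". Section 5.5 limits the count to the first cycle.

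**The concern.** One event falls under two handling rules with different eribulin doses. A site that looks up febrile neutropenia in Section 6.1 finds a same-dose rule. A site that starts from the DLT definition in 5.5.2 and follows its cross-reference in 6.2.1 finds a mandatory step down. Both sites would be following the protocol.

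A second, weaker problem concerns scoring. Section 6 files the event as hematological, but the hematological DLT list does not contain it. Someone scoring cycle 1 who takes the classification from Section 6 and checks only 5.5.3 would not count a DLT; someone who reads 5.5.2 would. The classification also affects reporting: Section 5.5.1 wants a suspected DLT reported within 24 hours, whereas the table in 7.5 gives 5 calendar days for a Grade 4 event. The automated DLT trigger described in 13.5 likewise needs a single definition to work from.

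**Working it through.** The plan states no figure on this point, so there is none to reproduce. The check sets the rules side by side.

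**Step 1: is the event a DLT under 5.5.2?** An exclusion is needed only for something that would otherwise be in the class. By naming febrile neutropenia among its exclusions, 5.5.2 places it among non-hematological toxicities. The exclusion is graded 3. An attributable Grade 4 event therefore stays in the definition.

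**Step 2: what eribulin dose follows?** The dose levels come from the escalation table in Section 5.2. The 6.2.1 column assumes recovery within its 7-day limit.

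| Current level | 5.5.2 with 6.2.1 | 6.1.3 |
|---|---|---|
| Level 2 (1.4 mg/m²) | 1.1 mg/m² | 1.4 mg/m² |
| Level 1 (1.1 mg/m²) | 0.8 mg/m² | 1.1 mg/m² |
| Level 0 (0.8 mg/m²) | no further therapy (level 0 rule) | same dose only if the event is not a DLT; otherwise the level 0 rule applies |

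At levels 1 and 2 the gap is one full level:
- Level 2: 1.4 − 1.1 = 0.3 mg/m², and 0.3/1.4 = 21% of the current dose.
- Level 1: 1.1 − 0.8 = 0.3 mg/m², and 0.3/1.1 = 27%.

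At level 0 there is no separate conflict. The opening text of 6.1 settles it once DLT status is settled.

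**Step 3: is DLT status itself contradicted?** Only Section 5.5 defines DLT, and it counts an event that meets either 5.5.2 or 5.5.3. Omission from 5.5.3 does not remove an event that 5.5.2 already covers. Continuing at the same dose does not deny DLT status either, because 6.1.2 keeps the dose, with growth factor, after neutropenia that it calls dose-limiting. So 5.5.2 implies a DLT and no sentence denies it. What remains is that the filing in 6.1 and the gap in 5.5.3 point a reader the other way.

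**Step 4: when would inconsistent scoring change a dose decision?** Apply the rules in 13.1 with one first-cycle event left out or counted, in a patient with no other DLT.

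| Not counted → counted | Consequence |
|---|---|
| 0/3 → 1/3, first cohort | escalate, against add three patients |
| 0/3 → 1/3, later cohort | none; both add three patients |
| 1/3 → 2/3 | add three patients, against go down a level (or stop at the lowest) |
| 0/6 → 1/6 | none |
| 1/6 → 2/6 | level acceptable, against level fails |
| already 2 or more | none |

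The scoring question bears on the recommended phase II dose (RP2D) only in the pivotal rows.

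**The case against.** **A specific rule overrides a general one.** Item 6.1.3 names the event and its grade, while 6.2.1 is general. Letting 6.1.3 govern is a natural reading and may be what was meant. But no sentence gives it precedence, and 6.2.1 covers every 5.5.2 DLT without exception. The objection shows how the conflict might be resolved, not that the text resolves it.

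**The grade in the exclusion might attach to fever alone.** Febrile neutropenia would then be exempt at every grade and 6.2.1 would not apply. The same list has a bullet in which one Grade 3 plainly covers nausea, vomiting and dehydration together. The fever-only reading would also exempt Grade 4 infection. It is not the ordinary reading.

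**The handling rules act only on later cycles.** This stands. The dose conflict does not itself enter the first-cycle DLT count.

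**A stronger inference.** A reader might infer that the protocol contradicts itself on whether the event is a DLT at all, and that level 0 is left open. The documents do not support this. Section 5.5.2 covers the event, and 6.1.3 sits in a numbered list beside two items on dose-limiting cytopenias, under text about patients with DLT. The level 0 sentence stands above it in the same section.

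**Conclusion.** The handling rules are wrong as written. After an attributable Grade 4 febrile neutropenia that recovers in time, a patient at level 1 or 2 is directed to eribulin doses one full level apart, depending on which section is read. This rests on the text alone, with the Grade 3 qualifier read as covering the whole exclusion bullet.

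On DLT status the finding is narrower. Section 5.5.2 implies that the event counts, and the layout of 6.1 and 5.5.3 invites some readers not to count it. A miscount would alter a decision only in pivotal cases such as 1/6 against 2/6, and only if that patient has no other DLT.

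No probability is claimed. A reader might take the 5% febrile neutropenia incidence in Section 2.2 and work out how often a six-patient level would contain such an event. That figure comes from adults on single-agent eribulin and is not stated to be Grade 4 or first-cycle. The documents give no rate for the combination. The chance of seeing an event is also not the chance that a dose decision changes.

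**What to change.** - Reconcile 6.1.3 with 5.5.2 and 6.2.1 so that one handling rule applies to Grade 4 febrile neutropenia, with a cross-reference or a statement of precedence.
- State in Section 5.5 whether an attributable Grade 4 febrile neutropenia is a DLT. The existing level 0 rule then follows without further text, as does the reporting time.
- Align the automated DLT trigger in 13.5 with that statement.

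Which handling rule and which classification apply is for the sponsor to decide; none is proposed here. The cost is a wording amendment. The sample size, dose levels and escalation rules are unaffected.
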